4.4 Sample size calculation

RCT

The primary objective of the study is to realize an efficient allocation of resources to the available treatment options in advanced PD. For this, primarily an economic evaluation will be carried out and the sample size has been calculated accordingly. Society's willingness-to-pay (WTP) per Quality Adjusted Life Year (QALY) may be indicative of whether or not CLI is affordable compared to DBS. The Dutch Raad voor de Volksgezondheid (RvZ) reported a value of €80,000 per additional QALY in 2006 as a potential upper limit of affordability. Explicitly, the figure is reported by the RvZ as a potential, but also unofficial limit: it should

Version 7: 23-10-2019 16 of 48

not be taken as a definite one. Other arguments based on patient preference or access to health care should be taken into account as well. Considering that CLI may be a less invasive intervention and access to health care is easier to facilitate when two interventions can be provided, a more lenient upper limit for the extra societal costs per additional QALY may be appropriate here. We propose a sample size calculation based on a WTP per additional QALY of €120,000 (50% above the RvZ figure). Based on the net health benefit formula suggesting that differences in QALYs between the interventions should be larger than the difference in costs (i.e., €34,174 a year) divided by the maximum WTP (i.e., €120,000 per QALY) in order for one intervention to be accepted as more efficient than another intervention, CLI treatment should at least outperform DBS treatment by 0.2847 QALY per year. Based on literature data with comparable costs estimates, [6] we anticipate standard deviations (SD) for QALYs up to 0.35 and for total costs up to €10,000 (factoring in a 12-month follow-up and non-responders).

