To achieve 80% power and given a two-sided significance level of 0.05, up to 26 patients per group (or 52 in total) are needed to detect a difference of at least 0.2847 QALY for WTP-values up to €120,000 and a worst case scenario of zero correlation between costs and clinical effect, using a two-group t-test. Accounting for a possible dropout of 20%, we will randomize 66 patients (33 per group). With this sample size and given the same test conditions (power, type-I error rate, test chosen, drop-out rate) we are also able to detect a difference in mean PDQ-39 scores between both groups of 11.9, assuming an expected mean score of 32 in the DBS group and a standard deviation of 15.

Motivation for standard deviations for QALY

Literature data [8-10] show that the standard deviation for PDQ-39 scores from operated PD patients equals 15 points and that a 4 to 5 points difference is associated with a QALY difference of approximately 0.1,[16] suggesting a standard deviation for QALYs of up to 0.35.

Patient preference trial

We (conservatively) estimate that during the inclusion period a total of 180 patients (60% of the eligible patients) may decline to participate in the RCT, but are willing to take part in the preference observational study. Based on our clinical experience it is expected that 60% of these patients (n=108) prefers DBS, against 40% (n=72) preferring CLI.

When comparing the effect of DBS treatment of patients who express a preference for that treatment with the effect of DBS treatment in the randomised patients, and given the same test conditions (power, type-I error rate, two group t-test) we are able to detect a difference in

Version 7: 23-10-2019 17 of 48

mean PDQ-39 scores between both groups of 8,4, assuming an expected mean score of 32 in the randomized DBS group and a standard deviation of 15.

In case only 120 patients (40% of the eligible patients) agree to take part in the preference observational study, we are able to detect a difference in mean PDQ-39 scores between both DBS groups of 8,9.

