For normally distributed data means and standard deviation were presented, for non-normally distributed data medians and interquartile ranges. For the Hoehn & Yahr stage median and range were reported.

Analyses

Randomized controlled trial

Reported outcomes were presented in Table SAP2 (part A and B). The main publication consisted of analyses in the mITT population. The analyses in ITT, as-treated and per-protocol populations were presented in supplements.

Analysis of main clinical outcome

The main analysis regarding the clinical outcome was the between-group difference in change from baseline to 12 months follow-up in total PDQ-39 summary index score in the mITT population, using a two-group *t*-test. Additionally, a multiple linear regression analysis was performed taking into account the stratifying variable (level of experience of the treatment center) and (if necessary) clinically relevant baseline imbalances. To assess whether the baseline value of the PDQ-39 served as an effect modifier (meaning that the association between intervention and outcome differed according to baseline PDQ-39) an interaction term was used in the regression analysis. In case of a significant interaction term, the analysis was additionally performed in two separate strata: one with patients with a median PDQ-39 or below and the other with patients with a PDQ-39 above median.

Sensitivity analyses

Sensitivity analyses concerning missing data as described in the paragraph “Patient replacement and missing data” were performed in the mITT population. To further assess robustness of the mITT analysis for the main clinical outcome additional sensitivity analyses were performed.

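### If the treatment effect varies with baseline PDQ-39, the SAP plans to describe this only by a median split, although contrasts from the interaction model it already fits would be about 10–20% more precise

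*SAP*

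**What the plan says.** The SAP (Analysis of main clinical outcome) compares change in PDQ-39 from baseline to 12 months in the mITT population by a two-group t-test, with a multiple linear regression in addition. An interaction term in that regression asks whether the treatment effect depends on baseline PDQ-39. If the term is significant, the analysis is additionally carried out in two strata: "one with patients with a median PDQ-39 or below and the other with patients with a PDQ-39 above median".

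The SAP does not say whether the analysis repeated in the strata is the t-test or the regression. It gives no significance level for the interaction and no size for the mITT population or the strata. Neither that section nor Table SAP2 provides for a treatment effect from the interaction model at a stated baseline value.

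The planning figures are in protocol section 4.4: "up to 26 patients per group (or 52 in total) are needed", and "Accounting for a possible dropout of 20%, we will randomize 66 patients (33 per group"). The same section gives a detectable difference for the PDQ-39: "a difference in mean PDQ-39 scores between both groups of 11.9, assuming an expected mean score of 32 in the DBS group", with an SD of 15.

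**The concern.** The clinical question behind an interaction is at which level of impairment one treatment does better. A fitted continuous interaction answers this with all patients. The median split uses half of them for each estimate, reports one average effect per half, and places the cut wherever this trial's median falls. A later reader cannot carry that cut to another population.

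The split is also shown only after a significant interaction. A real but undetected interaction would leave nothing planned to be reported by baseline. At stake is the precision and usefulness of a supporting analysis in a small trial.

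**Working it through.** **1. The plan's own figures.** Inputs from protocol section 4.4: two-sided alpha 0.05, 80% power, two-group t-test, QALY difference 0.2847, "standard deviations (SD) for QALYs up to 0.35 and for total costs up to €10,000", willingness to pay €120,000 per QALY.
- SD of net health benefit = √(0.35² + (10,000/120,000)²) = 0.3598.
- n per arm = 2 × (1.960 + 0.842)² × 0.3598² / 0.2847² = 25.1, so 26.
- With 20% dropout, 26/0.8 = 32.5, so 33.
- For PDQ-39 at SD 15 and 26 per arm, the noncentral t gives a detectable difference of 11.89 (stated: 11.9).

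All three figures reproduce.

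**2. Size of the halves.** 26/2 = 13 per arm, or 33/2 = 16.5 with no losses. A median split does not balance the arms: in simulation at 26 per arm, the smaller arm in the lower half had a median of 12 patients and a 5th percentile of 9–10. At 13 per arm and SD 15, power for 11.9 points is 49%, and the difference detectable with 80% power is 17.2 points. At 16 per arm these become 58% and 15.4.

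**3. Split against model, by formula.** Both are evaluated at the mean baseline of a half, which lies √(2/π) = 0.80 SD from the overall mean if baseline is normal. Assumptions: SD 15 at both times, correlation r between baseline and 12 months, linear interaction. The slope of change on baseline is then r − 1.
- Residual variance: s² = 225(1 − r²).
- Model SE: s × √[(2/n)(1 + 2/π)].
- SE of the t-test in a half: s_h × √[2/(n/2)], with s_h² = s² + (1 − r)²(1 − 2/π) × 225.

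Example with r = 0.5 and n = 26:
- s² = 168.75 and s_h² = 168.75 + 0.25 × 0.3634 × 225 = 189.2.
- Model SE = 12.99 × √(0.0769 × 1.6366) = 4.61.
- Split SE = 13.75 × √(2/13) = 5.40.
- Ratio = 1.17, so the model's SE is 15% smaller.

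| r (assumed) | Split SE | Model SE | Ratio | SE reduction | Simulated SE ratio |
|---|---|---|---|---|---|
| 0.2 | 6.43 | 5.21 | 1.23 | 19% | 1.21 |
| 0.5 | 5.40 | 4.61 | 1.17 | 15% | 1.16 |
| 0.7 | 4.33 | 3.80 | 1.14 | 12% | 1.14 |
| 0.9 | 2.59 | 2.32 | 1.12 | 10% | 1.12 |

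**4. Split against model, by simulated CI width.** Assumptions: 26 per arm, baseline SD 15, residual SD 14, effect changing 0.5 point per baseline point, 4,000 trials. With slopes of −0.25 and +0.25 in the two arms, the mean 95% CI widths are:
- t-test in the upper half: 22.9 points
- model at the upper-half mean: 20.3 points (ratio 0.884, so 12% narrower)
- model at the 75th percentile: 19.0 points

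With the reference-arm slope varied from 0 to −0.75, the matched reduction at the upper-half mean is 12–16%. The interaction test has about 44% power in this setting.

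**5. If the regression is what is repeated.** With baseline adjusted for within each half, the split's SE is about 1.12–1.13 times the model's, and the model's CI is about 13–14% narrower. The advantage does not depend on which reading of the SAP is taken.

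**The case against.** The strongest reply is that this is a conditional, secondary step. The SAP reserves its significance claim for the main clinical outcome, and no sample size, alpha or primary conclusion depends on the split. That stands, and it limits the point to a reporting improvement.

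Three stronger readings are tempting, and the documents do not support them:
- **That the split replaces the interaction model.** The SAP performs it additionally. What is missing is a plan to report effects from the model.
- **That the model gives the same information.** It does so only if the effect changes linearly with baseline. The stratum estimates do not need linearity across the whole range, which is a fair reason to keep them as a simple check.
- **That the gain is about 17%, worth about 46% more patients.** That compares the model at the 75th percentile (0.67 SD above the mean) with a t-test centred on the upper-half mean (0.80 SD above). A model CI is narrower nearer the centre, so part of that gain comes from the choice of point. At the matched point in the main scenario it is 12%, or 1/0.884² = 1.28, about 28% more patients.

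The figure of 13 per arm is also only a planning figure. The split is made in the mITT population, which excludes patients who refused their allocation and has missing PDQ-39 values imputed. Actual numbers may be higher or lower, and unequal between arms. Nor is the model-based estimate precise in absolute terms: a CI of about 20 points is still wide.

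**Conclusion.** The point holds as a minor improvement to a supporting analysis. The SAP fits an interaction model but plans to describe its consequence only through a data-dependent median split, and only after a significant result. Contrasts from the model are more precise in every case computed: CIs about 12–16% narrower in simulation, and standard errors about 10–19% smaller over correlations of 0.9 down to 0.2.

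These figures rest on a linear interaction, a normally distributed baseline and SD 15. The residual SD, interaction size and correlation are assumptions, since the documents give none of them, so a range is the most that can be claimed. A reader might infer that the trial's main comparison is weakened. It is not, because the primary t-test, sample size and alpha do not involve this step.

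**What to change.** In the SAP, Analysis of main clinical outcome, specify the regression with treatment, baseline PDQ-39 and their interaction. Report the treatment difference with 95% CI at the 25th, 50th and 75th percentiles of baseline PDQ-39, giving those values in points. Add a plot of the difference with its confidence band over the observed range. Do this whether or not the interaction is significant. Keep the median split as a descriptive check only, and state whether the t-test or the regression is repeated in the halves.

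The cost is a few sentences of SAP text and one figure, with no new data. The downside is reliance on linearity, which the plot and the retained split help to check.

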12.3 Motivation for outcome measures

To date, in most studies evaluating invasive treatments in advanced PD, the outcome is based on the recording of PD symptoms with the MDS-UPDRS, the time being in ONphase, the level of physical disability or perceived quality of life as measured with the PDQ-39. The mechanisms of action and procedures of both therapies are very different. For example, DBS treatment includes neurosurgery, implantation of stimulation equipment, and tuning of DBS-parameters in combination with gradual adjustments of the medication-schedule. In DBS, OFF-phase symptoms improve; and patients may experience this as more ON-phase time. DBS may influence behaviour and mood. In case of CLI, patients have a percutaneous endoscopic gastrostomy (PEG). During chronic CLI treatment, the pump has to be started every morning, it has to be removed every night, the PEG-stoma needs continuous care, and there is no change regarding OFF-phase symptoms, but OFF-phase time decreases and ON-phase time increases. The pump weights 0.5 kg. Considering all these aspects and patients' preferences, using OFF-phase parkinsonism, time being in ON-phase, or physical disability as a primary outcome would be inadequate. Therefore we have chosen to use patient-reported perceived quality of life -- measured with the PDQ-39 -- as a primary clinical outcome and as the effect measure to be linked with costs in the cost-effectiveness analysis. In addition, the cost per QALY was chosen as the outcome measure of the cost-utility analysis to allow for comparisons of results from economic evaluations of different interventions within and across different disease populations and different health sectors. The EQ-5D will be applied as the utility measure.

Version 7: 23-10-2019 42 of 48

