12.4 Assessment schedules

	Visit 1 Baseline	Visit 2	Visit	Visit 4	Visit 5	Visit 6	Visit	Visit 8
	Daseille	1wk	3mo	6mo	9mo	12mo	, 24mo	36mo
Baseline characteristics	X							
EKG, CT/MRI brain	X							
blood analysis	Х					Х		
Medication	Х	Х	Х	Х	Х	Х	Х	Х
MDS-UPDRS motor score	Х					Х		
Clinical Dyskinesia Rating Scale (CDRS)	Х					Х		
Motor symptom diary (3 days)	X					Χ	Χ	Х
Non-motor symptom checklist	Χ					Х	X	Х
Impulsive compulsive (QUIP)	Χ					Х		
Apathy scale Starkstein (AS)	X					Х		
Neuropsychological examination (incl. Mattis Dementia rating scale)	X					X		X
Mini-International Neuropsychiatric Interview	Х					Χ		
Psychiatric assessment	X					Х		
Hoehn and Yahr stage	X					X	Χ	Х
AMC disability scale (ALDS)	X					Х	X	Х
PDQ-39	X				Х	Х	X	X
EQ-5D	X	X	Х	Х	Х	Х	X	X
Treatment preference	X							
Treatment satisfaction						Х	Х	Х
Satisfaction with life scale	Х					Х	Х	X
Treatment failures		X	Х	Х	Х	Х	Х	Х
Side effects/adverse events/complications		X	X	Х	Х	Х	X	Х
Crossover to other treatment			Х	Х	Х	Х	Х	X
iMTA Medical Consumption Questionnaire (iMCQ)	X		X	X	Х	X	X	Х
iMTA Productivity Cost Questionnaire (iPCQ)	X		X	X	Х	Х	X	X
Use of (informal) care	Χ		X	X	X	X	Х	Х
Caregiver burden	Х		Χ	Χ	Χ	Χ	Х	X

Version 7: 23-10-2019 43 of 48

Table 2: assessment schedule patient preference trial

	Visit 1 Baseline	Visit 2 9mo		Visit 4 24mo	Visit 5 36 mo
Baseline characteristics	Х				=
Medication	X	Х	Х	Х	X
Hoehn and Yahr stage	Х				
PDQ-39	Х		Х	Х	X
Treatment preference	Х				
Treatment satisfaction			Х	Х	X
Side effects/adverse events/complications		Х	Х	Х	X
Treatment failures and cross-over		Х	Х	Х	X

Version 7: 23-10-2019 44 of 48

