- On-drug state time without troublesome dyskinesia -- mean hours per day in on-drug state without troublesome dyskinesia assessed with a 3-day motor symptom diary;
- Medication -- PD medication expressed in Levodopa Equivalent Daily Dose (LEDD, mg per day, including the continuous intrajejunal delivered levodopa)¹⁰;
- Functional health status -- Amsterdam Linear Disability Scale (ALDS) in on-drug state (29 items, score range 0-100) ¹¹;
- Cognitive performance -- Parkinson’s Disease Cognition Rating Scale (PD-CRS, score range 0-134) ¹²;
- Apathy -- Starkstein Apathy Scale (SAS, score range 0-42).¹³ Development of apathy was defined as newly scored apathy at 12-month follow-up (sum score ≥ 14 at follow-up and < 14 at baseline) and minimally 2 points increase in SAS score;

- Impulse-compulsive disorders and other compulsive behaviors -- Questionnaire for Impulsive-Compulsive Disorders in Parkinson's Disease (QUIP, utilizing established thresholds)¹⁴. Patients were considered to have developed an impulsive compulsive disorder, other compulsive behavior or compulsive use of medication if the QUIP criteria were met at 12-month follow-up and not at baseline. Impulsive compulsive disorder, other compulsive behavior or compulsive use of medication were considered to be resolved in case the QUIP criteria were not met at 12 months whilst they were fulfilled at baseline;
- Psychiatric diagnoses -- current and previous psychiatric diagnoses were assessed with the following subsets of the Mini International Neuropsychiatric Interview (MINI): major depressive episode, (hypo)manic episode, panic disorder, agoraphobia, social anxiety disorder, obsessive-compulsive disorder, alcohol use disorder, substance use disorder, and psychotic disorder.¹⁵ A new psychiatric diagnosis was defined as a current psychiatric diagnosis at 12-month follow-up, not being present at baseline. A psychiatric diagnosis was considered to be resolved in case it was present at baseline and not at 12-month follow-up;
- Harms -- (serious) adverse events ((S)AEs);
- Treatment course -- stopping the allocated treatment and switch to the alternative after initially receiving the allocated treatment (*i.e.*, switch from DBS to CLI or vice versa);
- Treatment satisfaction – number of patients that would recommend their treatment to others.

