The difference between both treatment groups in the mean change from baseline to 12 months in total MDS-UPDRS part II and III was shown with 95% CI. Similarly, the difference between groups in mean change from baseline to 12 months in CDRS was shown, as well as the difference in mean change in total time in both off-drug state and on-drug state without bothersome dyskinesias as reported in the 3-day motor diary, the difference in mean change in usage of dopaminergic medication (LEDD), and ALDS in on-drug phase, all with 95% CI. Discontinuation of the allocated treatment or switch to the other treatment option were summarized using simple descriptive statistics. The change in cognition expressed in points on PD-CRS from baseline to 12 months was reported. For apathy, the numbers and frequencies of patients with apathy at baseline and after 12 months follow-up were shown. Moreover, the numbers and frequencies of patients who had developed apathy after 12 months (*i.e.*, no apathy at baseline, but presence of apathy after 12 months), was reported for both groups, including the difference between these frequencies and 95% CI. Similarly, numbers and frequencies of impulsive-compulsive disorders and, separately, of development of impulsive-compulsive disorders were shown, with difference and 95% CI of the latter. Additionally, the numbers and frequencies of resolution of impulse control disorders were reported for both groups as well as the difference and 95% CI. Psychiatric diagnoses were reported analogues to impulse-compulsive disorders.

The number of patients that would recommend their treatment at 12 months to others was reported and the difference in frequency between the treatment groups was reported with 95% CI.

We presented line listing of safety outcomes using counts and percentages. All (S)AEs, including death were reported for each treatment arm. See Table SAP3 for an overview of (S)AEs. The treatment course per group was expressed in number of patients stopping allocated treatment and number of patients switching to the alternative treatment.

Table SAP2. Main and secondary clinical outcomes at 12 months, mITT RCT population

Part A: continuous outcomes

Outcome	Within-treatment Change from Baseline to 12 Months								Between-Group Difference in Change from Baseline mean (95% CI)	P-value
	Baseline				Months					
	CLI		DBS		CLI		DBS			
no. of patients	mean ±SE	no. of patients	mean ±SE	no. of patients	mean ±SE	no. of patients	mean ±SE			

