Main clinical outcome										
PDQ-39 summary index score										P
Secondary clinical outcomes										
MDS-UPDR-III score in on-phase										NR
CDRS in on-phase										NR
Time in on-phase without troublesome dyskinesias (hr)										NR
Time in off-phase (hr)										NR
LEDD (mg per day)										NR
ALDS score in on-phase										NR
PD-CRS score										NR

ALDS: Amsterdam Linear Disability Scale, CDRS: Clinical Dyskinesia Rating Scale, CI: confidence interval, CLI: continuous intrajejunal levodopa infusion, DBS: deep brain stimulation, hr: hours, LEDD: Levodopa Equivalent Daily Dose, MDS-UPDRS: Movement Disorder Society's Unified Parkinson's Disease Rating Scale, mg: milligrams, NR: not reported, PD-CRS: Parkinson's Disease Cognitive Rating Scale, PDQ-39: Parkinson's Disease Questionnaire-39, SE: standard error

Table 2. Main and secondary clinical outcomes at 12 months, mITT RCT population
Part B: dichotomous outcomes

Outcome	Baseline		12 Months		Between-group Difference at 12 months	Development / resolution *		Between-group Difference in development / resolution*
	CLI	DBS	CLI	DBS	difference in proportion (95% CI)	CLI	DBS	difference in proportion (95% CI)
	n/total no. of patients (%)	n/total no. of patients (%)	n/total no. of patients (%)	n/total no. of patients (%)		n/total no. of patients (%)	n/total no. of patients (%)	
Apathy (SAS)								
Impulsive-compulsive disorder (QUIP)								
Psychiatric diagnosis (MINI)								
Patient would recommend treatment	-	-				-	-	-

CLI: continuous intrajejunal levodopa infusion, DBS: deep brain stimulation, MINI: Mini International Neuropsychiatric Interview, NA: Not applicable, NR: not reported, SAS: Starkstein Apathy Scale, SE: standard error, QUIP: Questionnaire for Impulsive-Compulsive Disorders in Parkinson's Disease

* the first number relates to development of the outcome, the second number relates to resolution of the outcome (if applicable)

Table SAP3. (Serious) Adverse Events

	CLI- RCT (n)	DBS-RCT (n)	CLI-observational (n)	DBS-observational (n)
Serious Adverse events				
Death (n,%)				
Related to therapy (n,%)				
Other causes (specified, n,%)				
Hospital admission (n,%)				
Related to therapy (n,%)				
Other reason (specified n,%)				
Other SAEs (n,%)				
Specified (n,%)				
Adverse events				
Gastro-intestinal related (n,%)				
Specified (n,%)				
Polyneuropathy (n,%)				
Cerebral hemorrhage (n,%)				
Related to therapy (n,%)				
Epilepsy (n,%)				
Other (n,%)				
Specified (n,%)				

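### The apathy score (0-42) is compared between arms only after a cut at 14; adding a baseline-adjusted score row would recover information at little cost

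*SAP*

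**What the plan says.** The SAP's list of secondary outcomes names "Apathy -- Starkstein Apathy Scale (SAS, score range 0-42"). A patient has developed apathy if the change meets this rule: "sum score ≥ 14 at follow-up and < 14 at baseline) and minimally 2 points increase in SAS score". The schedule in Protocol 12.4 collects the scale in the randomised trial at baseline and 12 months only.

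Under Analysis of secondary clinical outcomes, the SAP states: "For apathy, the numbers and frequencies of patients with apathy at baseline and after 12 months follow-up were shown". The comparison follows in the next sentence. The proportion of each arm with new apathy "was reported for both groups, including the difference between these frequencies and 95% CI". Table SAP2 Part B, for dichotomous outcomes, holds the apathy row and adds a second contrast, under the column "Between-group Difference at 12 months".

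The same section gives MDS-UPDRS II and III, CDRS, diary times, LEDD and ALDS a between-group difference in mean change with 95% CI, and Table SAP2 Part A does the same for PD-CRS. The apathy score is not in Part A. It is also not among the outcomes that the SAP sets aside for separate publication. General principles limits P-values to the main clinical outcome; secondary outcomes get 95% confidence intervals only.

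**The concern.** The score is reduced to one side or the other of 14 before the arms are compared. A patient who moves from 13 to 15 counts in full as a new case. A patient who moves from 3 to 13, or from 15 to 30, does not. The month-12 proportion cannot tell a score of 15 from one of 30.

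The outcome has some interest here because Protocol 12.3 notes that "DBS may influence behaviour and mood", so a neuropsychiatric contrast between the therapies is plausible. With a few dozen patients per arm and no P-value, the interval is the whole result for apathy. If the effect is a general shift in score, an interval for a difference in proportions conveys less than the collected data allow.

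There is also a wording mismatch. The analysis section restates new apathy as absent at baseline and present at 12 months, without the 2-point minimum rise set under Secondary outcomes. A move from 13 to 14 is a new case under one wording and not under the other.

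**Working it through.** **Number of patients.** The documents state no figure for apathy, so the evaluable number is taken from Protocol 4.4 and checked first. The combined SD on the QALY scale is √(0.35² + (10,000/120,000)²) = 0.3598. Then n = 2 × (1.960 + 0.842)² × (0.3598/0.2847)² = 25.1, so 26 per arm, and 26/0.8 = 32.5, so 33 randomised per arm. Both match the protocol. For apathy, 26 per arm is used as the evaluable number and 33 as the upper case.

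**Assumed inputs.** The documents give no mean, SD, baseline to month-12 correlation or target difference for the apathy score. The central case assumes mean 10, SD 5.5, correlation 0.5, and the same 3-point rise for every patient in one arm.

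**Score analyses.**
- Change in score: SD = 5.5 × √(2 × (1 − 0.5)) = 5.5; SE = 5.5 × √(2/26) = 1.525; 3/1.525 = 1.97. The chance that the 95% CI excludes zero is about 49%.
- Month-12 score adjusted for baseline: SD = 5.5 × √(1 − 0.5²) = 4.763; SE = 4.763 × √(2/26) = 1.321; 3/1.321 = 2.27. The chance is about 60%, and 59% by simulation.

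**Month-12 proportion.** With whole-number scores, the rate at 14 or more is 1 − Φ((13.5 − 10)/5.5) = 26% without the shift and 1 − Φ((13.5 − 13)/5.5) = 46% with it.

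**Simulation, all four contrasts.** 20,000 trials; bivariate normal scores, rounded and held to 0-42; development defined with the 2-point condition; Newcombe intervals for proportions. Entries are the chance that the 95% CI excludes zero.

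| Scenario | New apathy | Month-12 proportion | Change in score | Baseline-adjusted score |
|---|---|---|---|---|
| Common 3-point shift, 26 per arm | 22% | 36% | 48-49% | 59% |
| Same, 33 per arm | 30% | 42% | 59% | 70% |
| 30% of one arm rise 10 points; mean 10, SD 5.5 | 23% | 31% | 38% | 45% |
| 30% rise 10 points; mean 8, SD 4.5 | 44% | 45% | 49% | 55% |
| 30% rise 12 points; mean 6, SD 4 | 70% | 71% | 64% | 69% |

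The last three rows use 26 per arm and correlation 0.5. Repeat runs differ by about one point. With no true difference, no method exceeded about 5%.

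**Share of information kept.** This is the ratio of required sample sizes under a common shift of 2.5 or 4 points, SD 5, mean 8 to 14 and correlation 0.3 to 0.7. Against the baseline-adjusted score, new apathy keeps 0.16 to 0.38 and the month-12 proportion 0.25 to 0.58. Against the unadjusted change score, the ranges are 0.18 to 0.57 and 0.29 to 0.88.

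**The case against.** The strongest reply is that the cut is a deliberate clinical choice. The SAP treats apathy, impulsive-compulsive disorders and psychiatric diagnoses alike, as presence or absence with new cases counted. New apathy is a readable harm, and the 2-point minimum excludes one-point crossings. Protocol 8.8 leaves the choice of method for secondary outcomes open. This stands as a reason to keep the proportions. It is not a reason to leave out the score, because QUIP and MINI yield criteria or diagnoses, whereas the apathy scale is a sum score like those in Part A.

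A reader might infer that the trial throws away most of its ability to show a difference in apathy. The documents do not support that. Table SAP2 also plans the month-12 proportion, which in the central case reaches 36% against 48-49% for change in score. About 10 of the points separating it from the adjusted score come from baseline adjustment, which the SAP plans for no secondary outcome, and not from removing the cut. The assumption that every patient shifts equally favours a comparison of means. When a subset develops marked apathy, the gap narrows and can close or reverse.

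A reader might also infer that the trial will probably report no difference in apathy because of the cut. That does not follow either. The plan reports an estimate with an interval, makes no significance claim for apathy and claims no power for it; a wide interval shows imprecision. Protocol 12.3 speaks of behaviour and mood and does not name apathy.

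**Conclusion.** The point holds as a minor one. A 0-42 score collected at both visits is compared between arms only as proportions after a cut at 14, and no comparison of the score is planned or deferred. Information is lost. If apathy shifts across the whole arm, the loss is substantial: about 22% and 36% for the two planned contrasts against 48-49% for change in score and 59% with baseline adjustment. If apathy appears sharply in a minority, the loss may be small or absent. These sizes rest on assumed values and an assumed effect pattern that the documents do not supply, so no single figure for the loss can be stated. The primary clinical and economic conclusions are not touched.

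**What to change.** Add one row to Table SAP2 Part A: the between-group difference in apathy score at month 12, estimated by linear regression on baseline score and arm, with 95% CI. Add a matching sentence to Analysis of secondary clinical outcomes. The adjusted form is preferred because the unadjusted change score does not reliably beat the month-12 proportion when the baseline to month-12 correlation is low (about 0.3).

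Keep the proportions with 14 or more and with new apathy in Part B, with their intervals, for clinical reading. Align the restated definition of new apathy in the analysis section with the 2-point condition under Secondary outcomes.

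The cost is SAP wording and one table row; the scores are already collected. The downside is that a difference in points is less immediately clinical than a count of cases, which the retained proportions cover.
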